## 6. TRIAL DESIGN

This is a clinical study assessing the feasibility of detecting and sampling sentinel lymph nodes in rectal cancer patients using a magnetic nanoparticle tracer (Sienna+ or Magtrace, class IIa device, CE-approved in Europe). See Appendix A for a flow diagram of the study schema.

The study will be conducted in two phases. The first (ex-vivo) phase will assess the feasibility of detecting sentinel lymph nodes using tracer/SentiMag probe in patients undergoing radical surgery for rectal cancer. The second (in-vivo) phase will assess the feasibility of removing sentinel lymph nodes identified using tracer/SentiMag probe in patients undergoing less radical surgery for early rectal cancer.

Expected duration of patient participation is 2-3 weeks, from pre-operative tracer injection till discharge from hospital following rectal cancer surgery. Standard practice includes a pre-operative clinic visit for discussion, visit to the endoscopy unit for endoscopic assessment of the tumour pre-operatively and hospital admission for surgery. There will be one additional visit for an MRI scan. This will be performed on the same day as the endoscopy visit or on the day of surgery.

Screening of patients and provision of information about the study will occur during the pre-operative clinic visit. Consent will be taken on visit to the endoscopy unit and Sienna+ tracer will be injected during endoscopy. The Sentimag probe will be used during surgery and for second phase participants the sentinel lymph node will be removed. Pathological assessment of the removed specimen will be carried out after surgery. Patients will be monitored on the colorectal ward post-operatively until discharge.

During each stage data will initially be recorded in hard copy on CRF then transferred to a secure electronic record.

## 7. PARTICIPANT IDENTIFICATION

### **7.1. Trial Participants**

Participants diagnosed with rectal cancers that are operable and have no symptoms of intestinal obstruction.

### **7.2. Inclusion Criteria**

- Participant is willing and able to give informed consent (in English) for participation in the trial.
- Male or Female, aged 18 years and below 90 years of age.
- Diagnosed with operable rectal cancer.
- Discussion of case at the Oxford Colorectal Cancer MDT.
- For in-vivo phase: Early rectal cancer and absence of lymph node involvement on staging MRI scan.
- In the Investigator's opinion, is able and willing to comply with all trial requirements.

### **7.3. Exclusion Criteria**

The participant may not enter the trial if ANY of the following apply:

- Female participant who is pregnant or lactating.
- Known intolerance or hypersensitivity to iron or dextran compounds, magnetic tracers, or SPIOs.
- For ex-vivo phase for ICG injection: known intolerance of iodine
- For in-vivo phase: advanced rectal cancer or radiological nodal involvement on staging MRI scan
- Cancer involvement of anal sphincter complex on clinical, radiological or endoscopic assessment.
- Age less than 18 and greater than 90.
- Adults who are not able to give consent or who are deemed vulnerable.

## **8. TRIAL PROCEDURES**

Methodology training for investigators: At the start of the study, the principal investigators will undergo methodology training and practice the use of the hand held SentiMag probe device. The chief investigator will standardize the sentinel lymph node biopsy technique during this feasibility study.

Screening and preliminary discussion of research project with potential participant: During the standard pre-operative clinic visit patients who have been identified as potential participants will be screened and informed about the study by a clinician or colorectal specialist nurse. They will have an opportunity to ask questions and will be provided with an information sheet.

Informed consent: In the endoscopy unit a clinician will discuss the study further and take consent if the patient is willing to proceed. A letter will be sent to the participant's GP informing them of the study.

Endoscopic injection of tracer and post-injection monitoring: The magnetic tracer will be injected approximately 5 days before surgery during endoscopic assessment of the tumour. The rectal tumour

will be visualized by endoscopy, as per standard clinical practice. Up to 2ml tracer solution will be infiltrated systematically (in 4 quadrants) into the submucosa around the rectal tumour. After the procedure, patients will be monitored for 1 hour to ensure no hypersensitivity or adverse reactions occur and provided with a contact telephone number in case of any delayed reaction or side-effects on discharge.

MRI scan of pelvis: On the same day as the endoscopy unit visit or the day of surgery, patients will undergo an MRI scan of the pelvis. This will be done 2-3 hours after the endoscopic injection of tracer or on the day of surgery.

Rectal cancer surgery: Patients will undergo rectal cancer surgery according to their clinical indication. During surgery for the “ex-vivo” group, indocyanine green dye (ICG) will be injected near the tumour. At the conclusion of surgery the surgeon will make an assessment as to whether the tracer injection affected surgery, for example by causing inflammation in the tissue planes.

Intra-operative detection of the sentinel lymph node using the SentiMag probe and excision of the identified node (second part participants only): During rectal cancer surgery, following excision of the tumour, the surgeon will use the hand held SentiMag probe to identify the sentinel lymph node. This will then be dissected and removed for subsequent histological analysis.

Post-operative monitoring: Following surgery patients will be admitted to the colorectal ward for routine post-operative care. During this time they will be monitored and any adverse reactions or post-operative complications will be recorded. The patients’ participation in the study will cease when they are discharged from hospital.

Ex-vivo detection of the sentinel lymph node in the surgical specimen using the SentiMag probe (first part only): The SentiMag probe will be used to measure the distribution of the tracer and to identify the sentinel lymph node in the specimen removed during the standard surgical procedure. A Near InfraRed (NIR) imaging system will also be used to assess the specimen to detect the distribution of ICG as an adjunct to identifying lymph nodes.

Ex-vivo histological assessment of the surgical specimen: A colorectal pathologist will examine the tissue removed during surgery to identify all the lymph nodes present and whether or not they contain metastatic cancer deposits, according to standard practice. At the conclusion of the study the samples will be held in the cellular pathology department, in line with standard practice for diagnostic surgical specimens.

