## 2. SYNOPSIS

Trial Title	Feasibility study of sentinel lymph node mapping in rectal cancer	
Internal ref. no. (or short title)	SentiRect Study	
Trial Design	Feasibility: proof of principle	
Trial Participants	Rectal cancer patients	
Planned Sample Size	40 patients	
Treatment duration	Single pre-operative administration	
Follow up duration	2-3 weeks	
Planned Trial Period	12 months	
	Objectives	Outcome Measures/Endpoints
Primary	
Establish feasibility of identifying sentinel lymph node in rectal cancer:
 
[A] Adverse or hypersensitivity reactions after Sienna+ tracer injection in rectal cancer patients.
 
[B] Establish whether tracer is still present and detectable at the tumour injection site and in the lymph nodes at the time of surgery.
 
[C] Determine the impact of Sienna+ injection on subsequent
	
[A] Frequency of adverse or hypersensitivity reaction.
 
[B] Frequency of tracer being detectable at the tumour injection site and in the lymph nodes at the time of surgery.
 
[C] Surgeon's assessment of any difficulties encountered

	surgery (e.g. any difficulties due to discolouration or inflammation of tissue planes)	attributable to prior Sienna+ injection.

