Our research objective will be to assess the feasibility of using a magnetic non-radioactive iron-based tracer (Sienna+ or Magtrace) and a handheld magnetometer (SentiMag) to accurately define the position of sentinel lymph nodes in patients with operable rectal cancer. This technology has already been successfully used in breast cancer patients in a UK multi-centre trial (Thill et al, 2014). The tracer is non-radioactive and safe (there is an extremely low risk of a hypersensitivity reaction to iron-based compounds, magnetic tracer and superparamagnetic iron oxide (SPIOs)). Our research will be done in two stages. The first “ex-vivo” stage will involve mapping tracer activity in total mesorectal specimens from rectal cancer patients. These will be focused on patients with rectal cancers where standard radical surgery is recommended. In this group we will also inject indocyanine green dye (ICG) into the tumour during surgery to act as an adjunct to identifying the lymph nodes while we develop confidence with the SentiMag system. ICG is a widely-used dye with many applications in medicine, including SLN

identification, and has been used with some positive early results in rectal cancer (Cahill et al, 2012). The second stage would then involve an “in-vivo” study in patients with early rectal cancers (ERCs) that are suitable for TEM. We would use SentiMag technology to assess the feasibility and safety of SLNB in patients with ERC by taking lymph nodes with "peaks" of tracer activity from the mesorectum. After completion of this study, our intention will be to perform a clinical trial based on SLNB in rectal cancer patients.

There are no major ethical or legal issues associated with this study as SLNB is established in breast cancer practice. Our research will help to further define suitability for either localised or radical surgery in early rectal cancer patients.

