## **8.6. Subsequent Visits**

[Visit 1: clinic] Potential participants will be informed about the study by the study investigators or the colorectal nurse specialists at their initial hospital clinic visit with the operating surgeon. This is part of the clinical work-up of a patient and therefore would not involve an additional visit for the participant. This visit will take place approximately 2-3 weeks prior to surgery. Information will only be given to patients who are already aware of their diagnosis. Patient information sheets will be given to the patient at this stage. Patients will be screened using the inclusion and exclusion checklist.

[Visit 2: endoscopy suite] Surgeons assess rectal cancers by endoscopic means in order to plan surgery. This is part of normal practice and will not involve an additional visit for the potential participant. This usually occurs a week before surgery. Informed consent will be obtained from participants at this stage. During the endoscopic procedure the tracer will be injected around the rectal tumour. Patients will be monitored for 1 hour following this for any adverse effect of the injection.

[Visit 3: Radiology suite] Patients will have an MRI scan to assess tracer uptake into the mesorectum. This is not part of the standard routine care and will involve an additional hospital visit for the patient. This will be undertaken 2-3 hours after the endoscopic injection, on the same day as the endoscopy visit or prior to surgery on the day of surgery.

[Visit 4: Admission to hospital for surgery]: This is part of normal practice and will not involve an additional visit for the potential participant. Sentinel node sampling will take place after surgery from the resected specimen (“ex-vivo” phase) or during surgery (“in-vivo” phase). Participants will be monitored during their post-operative stay in hospital as part of normal practice. The incidence of post-operative complications will be recorded on discharge.

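### Adverse events are counted only to discharge, over a window that varies with hospital stay, and section 12.1 pools both phases, which dilutes node-removal complications and leaves later ones uncounted.

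*Combined protocol and SAP*

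**What the plan says.** **Length of observation.** The synopsis gives "Follow up duration 2-3 weeks". Section 6 defines the same period: "Expected duration of patient participation is 2-3 weeks, from pre-operative tracer injection till discharge from hospital following rectal cancer surgery". Section 8 closes it at the same point: patients' "participation in the study will cease when they are discharged from hospital". Section 8.6 has complications recorded at discharge, and section 11.4 runs the serious-event window from injection to discharge. Appendix B ticks adverse-event assessment only at Visit 2 (endoscopy) and Visit 4 (surgical admission).

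**Lead from injection to surgery.** Section 8: "The magnetic tracer will be injected approximately 5 days before surgery". Section 8.6, on the endoscopy visit at which the tracer is given: "This usually occurs a week before surgery". Section 8.6 also uses 2-3 weeks for a different interval, clinic visit to surgery: "This visit will take place approximately 2-3 weeks prior to surgery".

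**Analysis.** Section 12.1 sets the frequency of adverse, hypersensitivity or complication events as the count of events over everyone recruited. It gives no time at risk and no split by phase. Section 12.2 plans 20 patients having radical surgery (ex vivo) and 20 having the less invasive TEM (in vivo). Only the second group has a node dissected as an added study step (sections 6 and 8). Section 4 says that this stage will "assess the feasibility and safety of SLNB in patients with ERC".

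**The concern.** A safety proportion can be interpreted only if the reader knows how long each patient was watched. Here that time is set by the date of discharge, which depends on the operation and probably on the outcome, since a patient with a complication is likely to stay longer. The group with the extra procedure is probably watched for the shortest time after surgery, and its events are averaged with those of 20 patients who did not have that procedure.

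Section 4 states the intention to follow this study with a clinical trial of sentinel node biopsy in rectal cancer. The in-vivo complication rate is the safety figure that trial would need. As planned, it would be roughly halved by the denominator and would omit anything that first appears at home. A new complication that brings a patient back into hospital would also fall outside the section 11.4 window.

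**Working it through.** **Inputs.** Stated period 14-21 days (synopsis; section 6). Lead 5 days (section 8) or 7 days (section 8.6). Phase sizes 20 and 20 (section 12.2), and 20 + 20 = 40 agrees with the synopsis. Length of stay: not in the documents.

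**Step 1: can the stated 2-3 weeks be reproduced?** Window = lead + stay, so stay = window - lead.
- 5-day lead: 14 - 5 = 9 to 21 - 5 = 16 days.
- 7-day lead: 14 - 7 = 7 to 21 - 7 = 14 days.

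Without a stated stay, the figure can be neither reproduced nor refuted. It holds if stays are this long and fails if they are shorter.

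**Step 2: the window for a range of stays (all stays are assumptions).**

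| Stay (days) | Window, 5-day lead | Window, 7-day lead |
|---|---|---|
| 1 | 6 | 8 |
| 3 | 8 | 10 |
| 4 | 9 | 11 |
| 5 | 10 | 12 |
| 7 | 12 | 14 |
| 10 | 15 | 17 |
| 14 | 19 | 21 |

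With TEM stays of 1-3 days and radical-surgery stays of 7-14 days, the windows are 6-10 and 12-21 days. At a common lead the ratio runs from 14/10 = 1.4 to 19/6 = 3.2. With TEM stays of 1-4 days and radical stays of 5-10 days, they are 6-11 and 10-17 days. In both sets TEM patients fall short of 14 days, while the radical group can reach it.

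**Step 3: what unequal windows do to a proportion.** Suppose both phases have the same constant risk, 10% per 14 days. The proportion seen in a window of w days is 1 - 0.9^(w/14).
- Radical surgery: w = 12 gives 8.6%; w = 21 gives 14.6%.
- TEM: w = 6 gives 4.4%; w = 10 gives 7.2%.

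Identical risk gives visibly different proportions. The pooled figure also moves with stay: (8.6% + 4.4%)/2 = 6.5% for stays of 7 and 1 days with a 5-day lead, and (14.6% + 6.5%)/2 = 10.6% (from unrounded values) for stays of 14 and 2 days with a 7-day lead. A constant risk is a simplification; surgical complications would cluster after the operation, which is the part of the window that differs.

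**Step 4: the denominator, whatever the stay.** Two node-removal complications: 2/20 = 10% in vivo, but 2/40 = 5% under section 12.1. With no events, the one-sided 95% upper bound is 1 - 0.05^(1/40) = 7.2% for 40 patients and 1 - 0.05^(1/20) = 13.9% for 20. For node removal only the second applies, and only to events before discharge.

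**The case against.** A reader might infer that the protocol promises 2-3 weeks of follow-up and then breaks the promise by stopping at discharge. The documents do not support that. Section 6 defines the period as ending at discharge and calls it expected, so no fixed 14-21 days was undertaken. A conflict arises only if stays are below about 7-9 days, which the documents neither state nor exclude. For radical surgery the assumed ranges overlap 14-21 days.

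A reader might also infer that complications of node removal are not captured at all. They are. Section 11.1 counts events from any protocol procedure, section 11.3 records all adverse events whether or not attributed to the device, and section 12.1 names complications in its frequency. What is absent is a result specific to node removal: section 5 ties primary endpoint A to tracer injection, and in-vivo endpoint E counts nodes found and removed.

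Four further points stand, and they limit the size of the problem. Tracer reactions are little affected, because both phases have the same one-hour monitoring, contact number and pre-operative interval. Device-related events already begun are followed until resolved or stable, and serious events to resolution (sections 11.3 and 11.4). No between-phase safety comparison is planned. Nothing in section 12.1 forbids an additional breakdown by phase.

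None of this helps with an event that starts after discharge. Appendix B schedules no contact then, and the telephone number in section 8 is given after endoscopy for delayed tracer effects.

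**Conclusion.** The point holds in a limited form. From the text alone: new adverse events are sought only to discharge, the window has no fixed length, and section 12.1 pools 40 patients although only 20 have the added node removal. With equal phases, pooling halves any node-removal complication rate (10% becomes 5%), and this needs no assumption about stay.

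That the window is shorter in vivo is an inference from TEM being described as less invasive. The figures of 6-10 against 12-21 days, and the proportions derived from them, rest on assumed stays and a constant risk. The post-discharge gap is certain in the plan, but its yield in events cannot be estimated from the documents. For a 40-patient feasibility study this is worth correcting because the correction is cheap; it does not undermine the assessment of early tracer reactions.

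**What to change.** 1. **Section 12.1, reporting.** Give adverse events and complications separately for each phase (planned denominator 20 each), with the days observed per patient summarised beside each rate. Keep tracer reactions apart from surgical and node-removal complications. Report node-removal complications as an in-vivo result. This costs wording only.
2. **Window.** Count events over one fixed number of days from injection for every patient, for example 21 days, the upper end of the stated range, completed by a hospital-record check. Align sections 8, 8.6 and 8.8 and Appendix B, and say in 11.4 whether the serious-event window moves with it. The cost is one record check for each of 40 patients, with the protocol amendment. Counts may rise slightly, and events managed elsewhere may still be missed, which the report should acknowledge.
3. **If discharge stays the cut-off.** State that the rates cover in-hospital events only, and still report by phase.

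In either case, reconcile the durations in the synopsis and sections 6, 8 and 8.6: the lead of 5 days or a week, and the 2-3 weeks used both for injection to discharge and for clinic to surgery.

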## **8.1. Recruitment**

The identification of patients suitable for this study will take place at colorectal cancer multi-disciplinary meetings. This will involve reviewing the clinical, histological and radiological investigations with other surgeons, oncologists, radiologists and pathologists as part of the normal clinical review process. The principal investigators, who are part of the standard clinical care team for rectal cancer patients, are routinely present at this meeting.

Identified potential participants will then be approached by the principal investigator during their routine pre-operative clinic visit, and screening will be performed at this time using a checklist. They will be

provided with an information sheet and given time to ask questions. Patients agreeing to participate will be recruited on their subsequent pre-operative visit to the endoscopy unit.

## **8.2. Informed Consent**

The participant must personally sign and date the latest approved version of the Informed Consent form before any trial specific procedures are performed.

Written and verbal versions of the Participant Information and Informed Consent will be presented to the participants detailing no less than: the exact nature of the trial; what it will involve for the participant; the implications and constraints of the protocol; the known side effects and any risks involved in taking part. It will be clearly stated that the participant is free to withdraw from the trial at any time for any reason without prejudice to future care, and with no obligation to give the reason for withdrawal.

The participant will be allowed as much time as wished to consider the information, and the opportunity to question the Investigator, their GP or other independent parties to decide whether they will participate in the trial. Written Informed Consent will then be obtained by means of participant dated signature and dated signature of the person who presented and obtained the Informed Consent. The person who obtained the consent must be suitably qualified and experienced, and have been authorised to do so by the Chief/Principal Investigator. A copy of the signed Informed Consent will be given to the participant and a copy will go into the patient's medical notes. The original signed form will be retained at the trial site.

## **8.3. Screening and Eligibility Assessment**

Not applicable. Participation will be sought from patients that are diagnosed with rectal cancer and are discussed at the Colorectal MDT meeting. A simple checklist of inclusion and exclusion criteria will be used to screen the patients during their pre-operative clinic visit.

## **8.4. Randomisation, blinding and code-breaking**

Not applicable

## **8.5. Baseline Assessments**

Confirmation of operable rectal cancer at the Oxford Colorectal MDT discussion.

## **8.6. Subsequent Visits**

[Visit 1: clinic] Potential participants will be informed about the study by the study investigators or the colorectal nurse specialists at their initial hospital clinic visit with the operating surgeon. This is part of the clinical work-up of a patient and therefore would not involve an additional visit for the participant. This visit will take place approximately 2-3 weeks prior to surgery. Information will only be given to patients who are already aware of their diagnosis. Patient information sheets will be given to the patient at this stage. Patients will be screened using the inclusion and exclusion checklist.

[Visit 2: endoscopy suite] Surgeons assess rectal cancers by endoscopic means in order to plan surgery. This is part of normal practice and will not involve an additional visit for the potential participant. This usually occurs a week before surgery. Informed consent will be obtained from participants at this stage. During the endoscopic procedure the tracer will be injected around the rectal tumour. Patients will be monitored for 1 hour following this for any adverse effect of the injection.

[Visit 3: Radiology suite] Patients will have an MRI scan to assess tracer uptake into the mesorectum. This is not part of the standard routine care and will involve an additional hospital visit for the patient. This will be undertaken 2-3 hours after the endoscopic injection, on the same day as the endoscopy visit or prior to surgery on the day of surgery.

[Visit 4: Admission to hospital for surgery]: This is part of normal practice and will not involve an additional visit for the potential participant. Sentinel node sampling will take place after surgery from the resected specimen (“ex-vivo” phase) or during surgery (“in-vivo” phase). Participants will be monitored during their post-operative stay in hospital as part of normal practice. The incidence of post-operative complications will be recorded on discharge.

